7.4 Safety Oversight

It is the responsibility of the Principal Investigator to oversee the safety of the study at his/her site. This safety monitoring will include careful assessment and appropriate reporting of adverse events as noted above, as well as the construction and implementation of a site data and safety-monitoring plan. Medical monitoring will include a regular assessment of the number and type of serious adverse events.

8 Source Documents and Access to Source Data/Documents

Source data is all information, original records of clinical findings, observations, or other activities in a clinical trial necessary for the reconstruction and evaluation of the trial. Source data are contained in source documents. Examples of these original documents, and data records include: hospital records, clinical and office charts, laboratory notes, memoranda, subjects' diaries or evaluation checklists, pharmacy dispensing records, recorded data from automated instruments, copies or transcriptions certified after verification as being accurate and complete, microfiches, photographic negatives, microfilm or magnetic media, x-rays, subject files, and records kept at the pharmacy, at the laboratories, and at medico-technical departments involved in the clinical trial.

The study case report form (CRF) is the primary data collection instrument for the study. All data requested on the CRF must be recorded. All missing data must be explained. If a space on the CRF is left blank because the procedure was not done or the question was not asked, write "N/D". If the item is not applicable to the individual case, write "N/A". All entries will be printed legibly in black ink.

Access to study records will be limited to IRB-approved members of the study team. The investigator will permit study-related monitoring, audits, and inspections by the IRB/EC, the sponsor, government regulatory bodies, and University compliance and quality assurance groups of all study related documents (e.g. source documents, regulatory documents, data collection instruments, study data etc.). The investigator will ensure the capability for inspections of applicable study-related facilities (e.g. pharmacy, diagnostic laboratory, etc.).

9 Ethics/Protection of Human Subjects

9.1 Ethical Standard

The investigator will ensure that this study is conducted in full conformity with Regulations for the Protection of Human Subjects of Research codified in 45 CFR Part 46, 21 CFR Part 50, 21 CFR Part 56, and/or the ICH E6.

9.2 Institutional Review Board

The protocol, informed consent form(s), recruitment materials, and all participant materials will be submitted to the IRB for review and approval. Approval of both the protocol and the consent form must be obtained before any participant is enrolled. Any amendment to the protocol will require review and approval by the IRB before the changes are implemented to the study. All changes to the consent form will be IRB approved; a determination will be made regarding whether previously consented participants need to be re-consented.

9.3 Participant and Data Confidentiality

Participant confidentiality is strictly held in trust by the participating investigators, their staff, and the sponsor(s) and their agents. Therefore, the study protocol, documentation, data, and all other information generated will be held in strict confidence. No information concerning the study or the data will be released to any unauthorized third party without prior written approval of the sponsor.

CONFIDENTIAL

This material is the property of the NYU School of Medicine and Langone Medical Center. Do not disclose or use except as authorized in writing by the study sponsor

The study monitor, other authorized representatives of the sponsor, representatives of the IRB or pharmaceutical company supplying study product may inspect all documents and records required to be maintained by the investigator, including but not limited to, medical records (office, clinic, or hospital) and pharmacy records for the participants in this study. The clinical study site will permit access to such records.

The study participant's contact information will be securely stored at each clinical site for internal use during the study. At the end of the study, all records will continue to be kept in a secure location for as long a period as dictated by local IRB and Institutional regulations.

Study participant research data, which is for purposes of statistical analysis and scientific reporting, will be transmitted to and stored at NYU Langone Medical Center. This will not include the participant's contact or identifying information. Rather, individual participants and their research data will be identified by a unique study identification number. The study data entry and study management systems used by clinical sites and by NYU Langone Medical Center research staff will be secured and password protected. At the end of the study, all study databases will be de-identified and archived at the NYU Langone Medical Center.

To further protect the privacy of study participants, a Certificate of Confidentiality will be obtained from the NIH. This certificate protects identifiable research information from forced disclosure. It allows the investigator and others who have access to research records to refuse to disclose identifying information on research participation in any civil, criminal, administrative, legislative, or other proceeding, whether at the federal, state, or local level. By protecting researchers and institutions from being compelled to disclose information that would identify research participants, Certificates of Confidentiality help achieve the research objectives and promote participation in studies by helping assure confidentiality and privacy to participants.

10 Data Handling and Record Keeping

10.1 Data Collection and Management Responsibilities

Data collection is the responsibility of the clinical trial staff at the site under the supervision of the site PI. The investigator is responsible for ensuring the accuracy, completeness, legibility, and timeliness of the data reported.

All source documents should be completed in a neat, legible manner to ensure accurate interpretation of data. Black ink is required to ensure clarity of reproduced copies. When making changes or corrections, cross out the original entry with a single line, and initial and date the change. **DO NOT ERASE, OVERWRITE, OR USE CORRECTION FLUID OR TAPE ON THE ORIGINAL.**

Copies of the electronic CRF (eCRF) will be provided for use as source documents and maintained for recording data for each participant enrolled in the study. Data reported in the eCRF derived from source documents should be consistent with the source documents or the discrepancies should be explained and captured in a progress note and maintained in the participant's official electronic study record.

Clinical data (including AEs, concomitant medications, and expected adverse reactions data) and clinical laboratory data will be entered into Redcap. The data system includes password protection and internal quality checks, such as automatic range checks, to identify data that appear inconsistent, incomplete, or inaccurate. Clinical data will be entered directly from the source documents.

10.2 Study Records Retention

Study documents will be retained for the longer of 3 years after close-out, 5 years after final reporting/publication, or 2 years after the last approval of a marketing application is approved for the drug

CONFIDENTIAL

This material is the property of the NYU School of Medicine and Langone Medical Center. Do not disclose or use except as authorized in writing by the study sponsor

for the indication for which it is being investigated or 2 years after the investigation is discontinued and FDA is notified if no application is to be filed or if the application has not been approved for such indication. No records will be destroyed without the written consent of the sponsor, if applicable. It is the responsibility of the sponsor to inform the investigator when these documents no longer need to be retained.

10.3 Protocol Deviations

It is the responsibility of the site PI/study staff to use continuous vigilance to identify and report deviations within 7 working days of identification of the protocol deviation, or within 7 working days of the scheduled protocol-required activity.

Protocol deviations will be reported to the local IRB per their guidelines. The site PI/study staff is responsible for knowing and adhering to their IRB requirements.

10.4 Publication and Data Sharing Policy

This study will comply with the NIH Public Access Policy, which ensures that the public has access to the published results of the research. This trial will be registered with clinicaltrials.gov as per the ICMJE policy, and the Section 801 of the Food and Drug Administration Amendments Act of 2007.

10.5 Data Safety and Monitoring

The definition of unanticipated problems (UP) involving risk to subjects or others according to the NYU SOM IRB Drug Trial Protocol template is any incident, experience or outcome that meets all of the following criteria: unexpected in nature, severity or frequency, related or possibly related to participation in the research, suggests that the research places subjects or others at greater risk of harm. The definition of an adverse drug event according to the NYU SOM IRB Drug Trial Protocol is any symptom, sign, illness or experience that develops or worsens in severity during the course of the study.

The DSMB will be made up of the Principal Investigator– [name] and Co-investigators- [name] and [name] All members of the DSMB are board certified physicians in their respective specialties.

The DSMB will review safety data after the first five enrolled subjects and every three months thereafter. All unanticipated problems that increase risk to the subjects will be reported to the IRB per NYUSOM IRB policy. The time frame for reporting SAE and UP to the DSMB is by telephone within 24 hours of awareness of the event. The time frame for reporting SAE and UP to the IRB is to submit reports promptly but no later than 5 working days from the time the investigator becomes aware of the event.

During these meetings, the DSMB will review and analyze any unanticipated problems or adverse events involving risk to the patient including any neurological damage, significant delay in physical therapy progress, local anesthetic toxicity or allergic reaction to Exparel etc.

Specific study stopping points is the occurrence of a serious adverse event such as a severe allergic reaction to Exparel. Additionally, after 5 patients in each group have completed all study related procedures, a brief safety analysis will be done by the Principal Investigator, [name], to check for evidence of systemic local anesthetic toxicity. Events will be reported to the anesthesia department QA.

Additionally, the DSMB will perform an interim safety and data analysis after 50 patients have completed all study related visits.

CONFIDENTIAL

This material is the property of the NYU School of Medicine and Langone Medical Center. Do not disclose or use except as authorized in writing by the study sponsor

11 Study Finances

11.1 Funding Source

Both Anesthesiology and Orthopedic Surgery will use departmental funds to provide the Exparel used for this study.

11.2 Costs to the Participant

There are no expected costs to the subjects.

This material is the property of the NYU School of Medicine and Langone Medical Center. Do not disclose or use except as authorized in writing by the study sponsor

14 Attachments

These documents are relevant to the protocol, but they are not considered part of the protocol. They are stored and modified separately. As such, modifications to these documents do not require protocol amendments.

14.1 Opioid Equivalents

Notes from Lamplot (2013)

Opioid and Route	Dose (mg)	Conversion Factor
Morphine IM/IV	10	1.0
Hydromorphone IM/IV	1.67	6.0
Hydrocodone oral	30	0.3
Tramadol oral	100	0.1
Oxycodone oral	20	0.5
Vicodin 5/500 oral	6 tabs	1.7

Equianalgesic Doses of Opioids²⁸

Opioid	Oral Equianalgesic Dose (mg)
Buprenorphine	0.3
Oxymorphone	1.5
Butorphanol	2
Hydromorphone	2
Oxycodone	7
Hydrocodone	10
Morphine	10
Methadone	10-20
Tramadol	40
Propoxyphene	43-45
Codeine	80
Meperidine	100

CONFIDENTIAL

This material is the property of the NYU School of Medicine and Langone Medical Center. Do not disclose or use except as authorized in writing by the study sponsor

14.2 PROMIS Assessments

Upper Extremities Short Form (Administered Pre-Operatively in Holding Area):

PROMIS[®] Item Bank v2.0 – Physical Function – Short Form 7a

Upper Extremity – Short Form 7a

Please respond to each question or statement by marking one box per row.

		Without any difficulty	With a little difficulty	With some difficulty	With much difficulty	Unable to do
PFA14r1	Are you able to carry a heavy object (over 10 pounds /5 kg)?	 5	 4	 3	 2	 1
PFA34	Are you able to wash your back?	 5	 4	 3	 2	 1
PFA36	Are you able to put on and take off a coat or jacket?	 5	 4	 3	 2	 1
PFB13	Are you able to carry a shopping bag or briefcase?	 5	 4	 3	 2	 1
PFB28r1	Are you able to lift 10 pounds (5 kg) above your shoulder?	 5	 4	 3	 2	 1
PFB34	Are you able to change a light bulb overhead?	 5	 4	 3	 2	 1
PFM16	Are you able to pass a 20-pound (10 kg) turkey or ham to other people at the table?	 5	 4	 3	 2	 1

CONFIDENTIAL

This material is the property of the NYU School of Medicine and Langone Medical Center. Do not disclose or use except as authorized in writing by the study sponsor

Global Health Short Form (Baseline Assessment)

PROMIS Scale v1.2 – Global Health Physical 2a

Global Health – Physical 2a

Please respond to each question or statement by marking one box per row.

		Excellent	Very good	Good	Fair	Poor
Global03	In general, how would you rate your physical health?	 5	 4	 3	 2	 1
		Completely	Mostly	Moderately	A little	Not at all
Global06	To what extent are you able to carry out your everyday physical activities such as walking, climbing stairs, carrying groceries, or moving a chair?	 5	 4	 3	 2	 1

Pain Intensity Scores:

PROMIS Item Bank v.1.0 – Pain Intensity – Scale

Pain Intensity – Scale

Please respond to each item by marking one box per row.

	In the past 7 days...	Had no pain	Mild	Moderate	Severe	Very severe
PAINQU6	How intense was your pain at its worst?....	 1	 2	 3	 4	 5
PAINQU6	How intense was your average pain?.....	 1	 2	 3	 4	 5
		No pain	Mild	Moderate	Severe	Very severe
PAINQU21	What is your level of pain right now?.....	 1	 2	 3	 4	 5

CONFIDENTIAL

This material is the property of the NYU School of Medicine and Langone Medical Center. Do not disclose or use except as authorized in writing by the study sponsor

14.3 Medication Usage Record

Medication Record for TSA Surgery

Thank you for participating in our research study and helping us improve pain control for patients undergoing total shoulder arthroplasty (TSA) surgery.

Patient: _____

Pain medication: **Percocet**

Please record the following information in the log below:

1. Time when you take your pain medication
2. How many pills you took at each time
3. Pain score on a scale of 0-10 (0 being no pain and 10 being the worst pain imaginable)
4. Any additional pain medications (such as Advil), therapies (such as ice packs) and side effects (such as itching or nausea).

Time	Number of pills of Percocet	Pain Score (scale of 0-10)	Additional pain medications, therapy or side effects

We will call you within 1-2 business days after surgery to ask for the above information. Additionally, participants can also scan, photograph and email the medication record to [name] at [contact]

Thank you for your participation.

CONFIDENTIAL

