This material is the property of the NYU School of Medicine and Langone Medical Center. Do not disclose or use except as authorized in writing by the study sponsor

List of Abbreviations

ASA	American Society of Anesthesiologist Score
VAS	Visual analog scale
TSA	Total Shoulder Arthroplasty
ISB	Interscalene Nerve Block
DVT	Deep vein thrombosis
ER	Emergency room
AE	Adverse event
SAE	Serious adverse event
IV	Intravenous
PO	Taken orally
PRN	Taken as needed
TID	Taken three times per day
Q4h	Taken every four hours
CI	Confidence interval
SD	Standard deviation; a parameter, which characterizes a population distribution
SE	Standard error
ANOVA	Analysis of variance; a linear model
NSAID	Non-steroidal anti-inflammatory drug

CONFIDENTIAL

This material is the property of the NYU School of Medicine and Langone Medical Center. Do not disclose or use except as authorized in writing by the study sponsor
Interventional Template Version: 28 APR 2017

Protocol Summary

Title	Liposomal Bupivacaine (Exparel®) Plus 0.5% Bupivacaine HCL versus 0.5 % Bupivacaine HCL for Interscalene Nerve Block (ISB) for patients undergoing Total Shoulder Arthroplasty (TSA)
Short Title	Understanding the effects of Exparel® on post-operative pain management and opioid utilization for patients undergoing TSA
Brief Summary	This is a phase IV, randomized, single-blind, single-center study comparing patient related outcomes such as postoperative pain and opioid usage for patients who receive ISB's containing liposomal bupivacaine (Exparel®) plus 0.5% bupivacaine HCL versus 0.5% bupivacaine HCL undergoing total shoulder arthroplasty.
Phase	Clinical study phase IV
Objectives	To compare opioid utilization and pain management of patients who receive Exparel in an ISB vs standard 0.5% bupivacaine HCL during the initial 72-hour post-operative period. Additionally, to understand the duration of block after addition of Exparel® to bupivacaine in an Interscalene block after TSA
Methodology	phase IV, randomized, single-blind, single-center study
Endpoint	
Primary Endpoints: Opioid utilization expressed as (oral morphine mg equivalents) during the initial 72-hour post-operative period.
 
Secondary Endpoints: Duration of opioid use Patient reported pain scores (VAS) Length of stay Reported long-term narcotic use at home Documented opioid refills Adverse events such as respiratory depression, hypoventilation, reintubation, nausea, constipation

Study Duration	3 years
Participant Duration	Four weeks

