Occupational and physical therapy progress and activity goals will be reviewed. As per standard of care, motor testing of the operated shoulder and arm will be assessed during these visits. This includes: No weight bearing exercises will be performed as per surgeon's instructions and the nursing staff will continue to obtain VAS pain scores.

[figure not shown]
During the 24-72 hour post-operative period, research staff will visit the patient while they are in the hospital to obtain and verify the pain medication taken. If the patient is discharged before the 72-hour period, the research staff will give the patient a copy of a medication record diary to complete. Additionally, the staff member will call the patient within 1-2 business days to obtain the remaining opioid utilization information.

After discharge, the research staff will continue to follow up with the patient on POD 7, POD 14 and POD 30 to assess pain scores, opioid usage patterns, and functional status. The pain intensity PROMIS assessment will be administered during each phone call. Additionally, on POD 30, participants will complete the Upper Extremity PROMIS form. Research staff will verify documented opioid refills through Epic and pharmacy records.

CONFIDENTIAL

This material is the property of the NYU School of Medicine and Langone Medical Center. Do not disclose or use except as authorized in writing by the study sponsor

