6.2 Analysis of Endpoints

Primary Endpoints:

Opioid utilization (expressed as oral morphine mg equivalents) used during initial 24-72 hours post-operative period after surgery.

Secondary Endpoints:

CONFIDENTIAL

This material is the property of the NYU School of Medicine and Langone Medical Center. Do not disclose or use except as authorized in writing by the study sponsor

Duration of opioid use
Patient reported pain scores (VAS)
Length of stay
Progress with physical therapy
Reported long-term narcotic use at home
Discharge location: home, acute rehab or skilled nursing facility
Documented opioid refills
Adverse events such as respiratory depression, hypoventilation, reintubation, nausea, constipation

The analysis of opioid use, VAS, and PROMIS assessments will rely on a univariate analysis of variance model for mean score. This model is in the class of models commonly known as unirep-ANOVA models. It assumes that the mean score is a function of elapsed time and the treatment regimen assigned. This model considers the fact that the subject's repeated measures are correlated. The fitted model will provide statistical estimates of the mean levels, the treatment-effect differences between mean levels, the standard deviation, the intra-class correlation coefficient, 95% CIs, standard errors (SE), and statistical hypothesis tests. The estimates of means will be used to compute summary criteria such as area under the curve (AUC) for each regimen. All estimates reported will be presented their 95% CIs.

All endpoints will be evaluated as fits the data set with graphical figures such as scatter plots, box-and-whisker plots, and frequency histograms to visualize the distribution of these outcomes and their relationships to covariates and treatment assignment. When appropriate descriptive graphical and tabular methods will also be estimated and presented in a graphical figure.

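### The home diary and its follow-up call do not reliably capture opioid use to 72 h in patients discharged early, and no required step completes the record after 72 h

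*Combined protocol and SAP*

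**What the plan says.** Section 6.2 defines the primary endpoint as opioid use in oral morphine mg equivalents, "used during initial 24-72 hours post-operative period after surgery". The Protocol Summary gives a different window, "during the initial 72-hour post-operative period". On either definition the window closes at 72 h.

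Section 3.1 has research staff verify medication while the patient is in hospital. For those who leave early it adds: "If the patient is discharged before the 72-hour period, the research staff will give the patient a copy of a medication record diary to complete". Then "the staff member will call the patient within 1-2 business days to obtain the remaining opioid utilization information". It does not say whether those days run from surgery or from discharge.

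The form in 14.3 does say: "We will call you within 1-2 business days after surgery to ask for the above information". The first item it asks patients to record is "Time when you take your pain medication". Its log has four columns: time, "Number of pills of Percocet", a 0-10 pain score, and one shared free-text column. The instruction for that last column is "Any additional pain medications (such as Advil), therapies (such as ice packs) and side effects". Patients may also send in a scan or photograph of the record, with no deadline.

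Section 3.1 schedules further calls on POD 7, 14 and 30 that cover patterns of opioid use, and a check of Epic and pharmacy records that is stated for refills. Under section 6.1, a patient whose 24-72 h opioid use cannot be established with reasonable certainty is excluded.

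**The concern.** To compute the endpoint, each dose needs a drug, an amount in mg and a position relative to surgery. The diary asks for a clock time but no date, and a tablet count but no strength. It does not ask for the name, mg and number of any other opioid. Other opioids are foreseeable: section 3.1 says the drugs given depend on pain level, and 14.1 lists conversions for hydromorphone, hydrocodone and tramadol.

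The call would be the natural place to repair these gaps, but on the form's timing it is often made before the window has closed. Section 2.2 expects the greatest benefit between 24 and 72 h, so the hours still to come are those in which the effect is sought. Under section 6.1 poor capture can then become exclusion after randomisation, which sits badly with the intention-to-treat statement in the same section.

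**Working it through.** **Inputs from the documents.** The window is 24-72 h (6.2). The call is one or two business days after surgery (14.3), or the same interval with no anchor (3.1). 184 are enrolled to give 146 evaluable (4.6).

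**Assumptions (not in the documents).** Surgery takes place Monday to Friday and ends between 10:00 and 18:00; calls are made between 09:00 and 17:00. Discharge on POD 1 and on POD 2 are shown as alternatives, because no discharge distribution is given.

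**Step 1: hours from surgery to a call on POD d.** Earliest = 24d + 9 - 18 = 24d - 9. Latest = 24d + 17 - 10 = 24d + 7.

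- POD 1: 15-31 h. POD 2: 39-55 h. Both are always before 72 h.
- POD 3: 63-79 h. This may be before 72 h.
- POD 4: 87-103 h. This and any later day are always after 72 h.

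**Step 2: POD of the first and second permitted call day.**

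| Surgery | From surgery (14.3) | From POD 1 discharge | From POD 2 discharge |
|---|---|---|---|
| Mon | 1, 2 | 2, 3 | 3, 4 |
| Tue | 1, 2 | 2, 3 | 3, 6 |
| Wed | 1, 2 | 2, 5 | 5, 6 |
| Thu | 1, 4 | 4, 5 | 4, 5 |
| Fri | 3, 4 | 3, 4 | 3, 4 |
| **Certainly before 72 h** | **7 of 10** | **3 of 10** | **0 of 10** |
| **May be before** | **1** | **3** | **3** |
| **After** | **2** | **4** | **7** |

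These are counts of weekday and lag combinations, not proportions of patients.

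**Step 3: how much of the window is still to come at an early call.** For a call at h hours the fraction is (72 - h)/48. At 24 h it is 48/48, the whole window. At 48 h it is 24/48, half. On the 0-72 h definition the fractions are 48/72 = 67% and 24/72 = 33%. These are hours not yet elapsed when the call is made; they become lost data only if nothing later completes the record.

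**Step 4: tablet strength.** MME per tablet is proportional to the oxycodone content. With an assumed content of 2.5 to 10 mg, the same pill count spans 10/2.5 = 4-fold in MME unless the strength is taken from another record.

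**Step 5: room for exclusions.** 184 - 146 = 38, and 38/184 = 20.7%. The 184 is consistent with an assumed 20% loss: 73/0.8 = 91.25, rounded up to 92 per arm, and 2 x 92 = 184. The 146 itself cannot be reproduced, because the plan states no alpha, power, effect size or SD.

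**The case against.** The strongest reply is that the diary is only one of several sources. Staff verify in-hospital doses, so the diary covers only the time after discharge. Nothing tells patients to stop logging after the call, and they may send the form in later. Staff can ask about dates and strengths by telephone, free text can hold another drug's name and dose, and strength should be on the prescription. The POD 7 call asks about opioids again. The section 3.1 call follows a sentence about discharge, so it may well count from there. Figures are missing from the text of sections 3.1 and 3.2 and might show timing.

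Much of this stands, and it rules out several stronger readings:

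- A reader might infer that the endpoint cannot be obtained at all for discharged patients. The other routes show that it can.
- A reader might take Step 3 to mean that 50-100% of the window is lost. That would need early discharge, the surgery anchor and no later completion of the record. The documents establish only the second, and only on the form.
- A reader might infer that a one-day dating error distorts the total by half. In an even, continuous log, a one-day shift moves as many doses in as out and leaves the net total unchanged. Clock times in a sequential log also roll over at midnight, so the day is ambiguous mainly when a whole day has no entry.
- A reader might infer that later doses depend on memory at POD 7. The diary is a contemporaneous record that the patient can consult or send.

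What the reply does not supply is a required step. Sending the form is optional and has no deadline, the POD 7 call is not said to complete the 72 h record, and the records check is stated for refills.

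**Conclusion.** The point holds in a limited form: as written, the form and its call do not reliably capture opioid use to 72 h in patients discharged early. On the form's own timing, both permitted call days fall at about 24-48 h for Monday-Wednesday surgery, and one of the two does for Thursday. That gives 7 of 10 combinations before 72 h and 1 more that may be. If section 3.1 is read as counting from discharge, the figures are 3 and 3 for POD 1 and 0 and 3 for POD 2. The two sections need reconciling whichever reading was intended.

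The missing date, strength and other-opioid prompts mean that placing doses in the window and converting them to MME depends on inference or on other records. How many patients would be affected cannot be estimated, because the documents give no distribution of surgery day, discharge day or call lag. The hour ranges rest on the assumed working hours. The conflict between the 0-72 h and 24-72 h windows is a separate matter that a better diary would not resolve.

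**What to change.** 1. In both section 3.1 and form 14.3, set the call or diary collection for the first business day at or after 72 h from surgery, with the same anchor in both, and state that this step completes the 72 h opioid record.
2. On the form, add a date column and a name/mg/number line for any other opioid. Have staff enter the dispensed tablet strength and print the patient's own 24 h and 72 h clock times at discharge.

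**Cost.** No visit, call or participant is added. Section 14 allows the form to change without a protocol amendment. The section 3.1 change needs IRB approval, and the form goes to the IRB as participant material (9.2). The form becomes slightly longer and the call later. For Wednesday surgery, 72 h falls on Saturday, so the call moves to Monday, POD 5, at about 5 x 24 = 120 h. Tuesday surgery that ends after Friday's calling hours moves to Monday, POD 6, at about 6 x 24 = 144 h. The dated diary must therefore carry the record over that interval. This is a cheap improvement.
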